#### 7.9 Withdrawal criteria

Patients can be withdrawn from the trial if:

- They withdraw their consent at any point during the study **for any reason**. This can happen at any time after consent and during follow up. In such an event no additional data will be collected from the patient and there will be no follow up. The study doctor will ascertain whether the patient wishes the withdrawal of consent to apply retrospectively to the withdrawal (i.e. can we use data already collected?). The outcome of any and all discussions regarding the withdrawal of consent will be documented in the medical notes and case report form.
- A patient's condition deteriorates due to heart failure or another pathology to the extent that they are expected to die within the next 24 to 48 hours.
- The study doctors deems the risk of continuation due to serious drug reactions or adverse events is too great to the patient. This will be fully discussed with the patient and the content and outcome of all discussions will be documented in the medical notes and CRF.
  - Worsening symptoms of heart failure\*
  - Hyponatraemia (<135 mmol/L)
    - Asymptomatic\*
      - Severe (<130 mmol/L)\*

    - Symptomatic (confusion, drowsiness, nausea or vomiting)\*\*
  - Hypotension
    - Asymptomatic\*
    - Symptomatic with no sequelae\*
    - Symptomatic with significant sequelae i.e. fall due to postural hypotension\*\*
  - o Hyperchloraemia
    - Mild 107 110 mmol/L\*
    - Severe >110mmol/L\*\*
  - Worsening renal function
    - >30% increase in serum creatinine from admission. \*
    - >50% increase in serum creatinine from admission.\*
    - >100% increase in serum creatinine from admission.\*\*
  - Side effects of acetazolamide: haemorrhage, ataxia, depression, diarrhoea, dizziness, fatigue, flushing, irritability, headache, loss of appetite, nausea, vomiting, taste disturbance, paraesthesia,
    - Tolerable to the patient.\*
    - Intolerable to the patient.\*\*

\* - Clinically relevant safety endpoint that would not automatically lead to the discontinuation of the study drug. Withdrawal would be at patient's request or the study doctor's discretion if the risk of continuation was deemed too high.

\*\* - Occurrence would lead to withdrawal from the study if it occurred in the acetazolamide arm

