# 9.2 Operational definitions for (S)AEs

Due to the pilot and exploratory nature of this study **all** adverse events and adverse reactions will be recorded. All serious adverse events serious adverse reactions, and suspected unexpected serious adverse reactions will be reported.. This will enable collection on safety data for the use of ACZ concurrently with high dose loop diuretics as well as data on the tolerability of treatment for a future trial.

	Asymptomatic hypotension (systolic blood pressure (SBP) <90 mmHg)
	Symptomatic hypotension (SBP <90 mmHg and symptoms of: dizziness or presyncope)
	Asymptomatic hyponatraemia (serum sodium concentrations <130 mmol/L)
Adverse Events	Symptomatic hyponatraemia (serum sodium concentrations <130 mmol/L and symptoms of fatigue, nausea, vomiting, or headache not promoting further treatment or investigation)†
	Flare of gout requiring oral treatment and analgesia
	Decrease in estimated glomerular filtration rate >50% of baseline value
	† Treatment of headache with analgesia not included in this definition however treatment of nausea or vomiting with antiemetic is.
	Symptomatic hypotension with sequelae (SBP <90 mmHg and symptoms of: dizziness or presyncope and fall or injury as a direct result)
	Symptomatic hyponatraemia with sequelae (serum sodium concentrations <130 mmol/L and symptoms of fatigue, nausea, vomiting, headache which prompt further treatment or investigation,† or confusion or seizure deemed secondary to hyponatraemia).
	Decrease in eGFR >100% of baseline value or serum creatinine >221µmol/L
	Deterioration in condition during trial defined as:
Serious Adverse Events	
 
Deemed to need escalating doses of loop diuretic or the addition of a second diuretic agent such as thiazide diuretic.
 
Deemed to need inotropic support
 
New diagnosis of infection
 
New diagnosis of another concurrent illness that will prolong hospital stay
 
Transition to end-of-life care
 
Death
 

	Overdose of ACZ or furosemide infusion defined as 1) >500mg given per day of ACZ or 2) >240mg IV furosemide per day.
Adverse Reactions	Metabolic acidosis bicarbonate <23 mmol/L
	Hyperchloraemia 107-110 mmol/L

	Teaching Hospi	tals
	Any of the following possible side effects of acetazolamide that are NHS tolerable to the patient: haemorrhage, ataxia, depression, diarrhoea,	Trust

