	dizziness, fatigue, flushing, irritability, headache, loss of appetite, nausea, vomiting, taste disturbance, paraesthesia.	
	Severe hyperchloraemia 107-110 mmol/L	
Serious Adverse	Severe metabolic acidosis bicarbonate <20 mmol/L	
Reactions	Any of the possible side effects of acetazolamide listed in the MHRA	
	approved SPC that are intolerable to the patient and lead to	
	investigations.	
Suspected Unexpected Serious Adverse Reactions	Any SAR that is not expected based on the MHRA SPC for acetazolamide in relation to the nature and severity of the SAR will be reported as SUSAR. Due to the lack of data on the safety and tolerability of acetazolamide in modern patients with heart failure treated with high dose loop diuretic we will consider any SAR that occurs in >5% of patients as a SUSAR	

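### Three thresholds are wrong or contradictory as written: the renal exclusion limit (30 or 20 ml/min), the chloride range graded as both a reaction and a serious reaction, and a renal SAE criterion that cannot be met

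*Protocol*

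**What the plan says.** **Renal exclusion.** The Trial Summary (exclusion item 11) excludes an eGFR of 30 ml/min or less by Cockcroft-Gault. Section 6 (exclusion item 10) uses the same formula and excludes 20 ml/min or less.

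**Chloride.** Section 9.2 lists "Hyperchloraemia 107-110 mmol/L" under adverse reactions and "Severe hyperchloraemia 107-110 mmol/L" under serious adverse reactions. It has no row for values above 110. Section 7.9 grades 107-110 as mild and has "Severe >110mmol/L" as a withdrawal event in the acetazolamide arm. The exclusion lists in the Trial Summary and section 6 also call chloride above 110 severe. Section 9.2 treats "any SAR that occurs in >5% of patients as a SUSAR", and section 9.4 adds that a non-serious reaction occurring in more than 10% of patients is handled the same way.

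**Renal events.** The AE row in section 9.2 reads "Decrease in estimated glomerular filtration rate >50% of baseline value". The SAE row reads "Decrease in eGFR >100% of baseline value", with a serum creatinine above 221 µmol/L as the alternative. Section 7.9 uses creatinine instead: ">100% increase in serum creatinine from admission" leads to withdrawal in the acetazolamide arm.

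**The concern.** The renal exclusion decides who may be randomised. Section 13.5 does not permit premeditated deviations, so enrolling a patient at, say, 25 ml/min complies with one page and breaches the other.

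The two rows in section 9.2 determine how an event is listed. They feed the SAE and SAR rates, which are secondary outcomes in section 3.5, and they inform the 24-hour reporting described in section 9.4. Chloride is a co-primary endpoint and the drug is expected to limit its fall, so this grading concerns the variable that acetazolamide is meant to move. Section 2.2 names renal dysfunction as a risk of the combination, yet the relative criterion meant to separate a serious renal event from a non-serious one has no effect.

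**Working it through.** **1. Renal exclusion.** The formula is the same in both places, so this is not a difference of units. The limits differ by 30 - 20 = 10 ml/min. The band above 20 and up to 30 ml/min is excluded by the summary and admitted by section 6. The protocol gives no figure for how many patients fall in it.

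**2. Chloride.** Side by side:

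| Place | 107-110 mmol/L | Above 110 mmol/L |
|---|---|---|
| 9.2, adverse reactions | listed | not listed |
| 9.2, serious adverse reactions | listed as severe | not listed |
| 7.9 | mild | severe, withdrawal (acetazolamide arm) |
| Summary and section 6 exclusions | not excluded | severe, excluded |

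The two rows in 9.2 overlap completely. Moving the serious row to above 110 leaves no overlap and agrees with every other place.

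Effect on the SUSAR trigger: the smallest count that exceeds 5% (serious reactions) against the smallest that exceeds 10% (non-serious reactions). Sections 9.2 and 9.4 speak of patients without naming an arm, so both readings are shown. Arm and total sizes come from section 10.1 (18 and 27 on acetazolamide; 35 and 50 in all) and the planned 40 from the Trial Summary.

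| Denominator | More than 5% | More than 10% | Shift |
|---|---|---|---|
| Acetazolamide arm, 18 | 1 (5.6%) | 2 (11.1%) | 1 |
| Acetazolamide arm, 27 | 2 (7.4%) | 3 (11.1%) | 1 |
| All patients, 35 | 2 (5.7%) | 4 (11.4%) | 2 |
| All patients, 40 | 3 (7.5%) | 5 (12.5%) | 2 |
| All patients, 50 | 3 (6.0%) | 6 (12.0%) | 3 |

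At 40 patients, 2/40 is exactly 5% and 4/40 exactly 10%, so neither exceeds its limit.

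**3. Renal SAE row.** After a fall of fraction f, eGFR = baseline × (1 - f). For f above 1 the result is negative at any baseline, so the eGFR limb is never met. The AE row (f above 0.5) is attainable: below 30 from a baseline of 60, and below 45 from 90.

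Only creatinine above 221 µmol/L remains. Compare it with the doubling in section 7.9, which counts from admission:

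- Doubling reaches the absolute limit at an admission value of 221 / 2 = 110.5 µmol/L. Below that there is a gap.
- Admission 80: 2 × 80 = 160. Values above 160 and up to 221 (221 / 80 = 2.76, a rise of up to 176%) mean withdrawal in the acetazolamide arm but do not meet the SAE row.
- Admission 100: 2 × 100 = 200. Values above 200 and up to 221 (221 / 100 = 2.21, up to 121%) do the same.

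No eGFR formula is needed for these figures. One is needed to ask whether such a patient meets the AE row, and section 9.2 names none. Assume eGFR is proportional to creatinine to the power -k. A doubling is then a fall of 1 - 2^(-1) = 50.0% for k = 1 and 1 - 2^(-1.2) = 56.5% for k = 1.2. A rise of more than 100% is thus a fall of more than 50%, provided the admission and baseline values are close.

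**The case against.** The best defence is that little depends on the section 9.2 rows alone. Seriousness and causality are judged by the investigator under sections 9.1 and 9.4, including prolonged hospitalisation and other important medical events. Section 9.3 requires clinically significant laboratory values to be recorded, and section 7.9 withdraws acetazolamide patients at chloride above 110 or a creatinine rise above 100%. A patient whose creatinine doubles would generally still be recorded under the AE row. All of this stands. A reader might infer that serious renal injury or severe hyperchloraemia would go unrecorded, or that these rows alone decide 24-hour reporting. The documents do not support either reading.

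The chloride entry also looks like a copying slip. Its intended value can be recovered from three other places, and it errs on the cautious side. That too stands, but staff apply what is printed, and as printed the SAR rate counts values that section 7.9 calls mild.

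Finally, the summary list is headed as the main criteria only, and a site would ordinarily work from section 6. This softens the eligibility conflict without removing it: a summary may omit a criterion, but this one states a different limit.

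**Conclusion.** All three discrepancies are in the current text and should be fixed, but they do not weigh the same.

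- The eligibility conflict matters most. It covers the whole band above 20 and up to 30 ml/min, and the document does not show which limit was meant. How many patients it affects cannot be stated.
- The chloride grading inflates the SAR rate and applies the 5% trigger in place of the 10% one. The shift is 1 patient on acetazolamide-arm numbers and 2 to 3 on all patients. A single figure would assume a denominator that the protocol does not give: section 3.5 reports these rates for the treatment arm but does not define the trigger.
- The renal SAE row has one limb that cannot be met. The resulting gap is confined to admission creatinine up to about 110 µmol/L with a peak of 221 or less. That the AE row generally catches such a patient rests on eGFR varying at least inversely with creatinine and on similar admission and baseline values.

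The last two are smaller corrections with back-ups elsewhere. Nothing here changes the sample size or the primary analysis method.

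**What to change.** 1. Choose one Cockcroft-Gault limit and state it in both the Trial Summary and section 6, before recruitment.
2. In section 9.2, set the serious chloride row to above 110 mmol/L and keep 107-110 as a non-serious adverse reaction.
3. Replace the impossible eGFR limb with an attainable relative criterion, such as the creatinine rise above 100% already used in section 7.9. Make the AE cut milder at the same time: a creatinine doubling is about a 50% eGFR fall, so the new SAE limb would otherwise coincide with the present AE row. The exact cuts are for the sponsor to choose.

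The cost is one protocol amendment and an update of the CRF and SAE form.

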# 1 BACKGROUND

The cornerstone of treatment for congestion in patients with heart failure is loop diuretics such as furosemide or bumetanide, but failure to respond or worsening despite increasing dose of diuretic - diuretic resistance - is common. Current guidelines recommend the addition of a thiazide (or thiazide-like) diuretic (e.g. bendroflumethiazide or metolazone) when a patient has become 'resistant' to loop diuretics. However, only a few small studies have tested the effects of thiazide and thiazide-like diuretics in patients with heart failure with inconsistent results.

Loop and thiazide diuretics prevent sodium reabsorption in the loop of Henle and distal tubule but the majority of renal sodium reabsorption (~70%) occurs in the proximal tubule. Reabsorption of sodium in the proximal tubule depends predominantly on the sodium-hydrogen (Na+/H+) antiporter. Carbonic anhydrase catalyses the interconversion between carbon dioxide and water on the one hand, and hydrogen (H+) and bicarbonate ions on the other. Increased intracellular H+ concentration promotes sodium reabsorption in the proximal tubule by increased activity of Na+/H+ antiporters. Thus carbonic anhydrase inhibitors (such as acetazolamide) reduce sodium reabsorption in the proximal tubule and act as a diuretics.

Early studies of acetazolamide in the 1950-60s in patients with heart failure, before the advent of loop diuretics, found that high dose acetazolamide (>1000mg per day) used alone was less effective than standard of care at the time (intramuscular mercurial diuretics). However, more recent studies have found that acetazolamide at doses between 250-750mg daily may have both natriuretic and diuretic effects when used in combination with loop diuretics or spironolactone, and may have a greater diuretic effect than thiazide diuretics.

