# 3.2 Primary objective

# Primary hypothesis

The addition of 250mg acetazolamide orally twice-daily to 240mg / 24hr IV furosemide infusion willNHS Trust increase diuresis while also reducing the amount by which serum chloride concentrations fall during diuresis in a patient admitted to hospital for venous congestion due to heart failure compared to furosemide infusion alone.

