# 3.5 Secondary endpoints/outcomes

All secondary endpoints are exploratory designed to inform future research.

Differences between the two groups during the 4 day treatment period in:

1) daily weight

2) serum electrolyte levels (sodium, bicarbonate and potassium)

3) incidence of electrolyte abnormalities; hyponatraemia (<135 mmol/L), hypochloraemia (<96 mmol/L), hypokalaemia (<3.5 mmol/L), high (>30 mmol/L) or low (<22 mmol/L) serum bicarbonate.

4) change in renal function measured by serum creatinine (µmol/L) and estimated glomerular filtration rate (eGFR) (ml/min/1.72m2)

5) change in urinary electrolyte levels after 48 and 96 hours of treatment; sodium, chloride, potassium.

- 6) clinical assessment of congestion
- 7) ultrasound measures of congestion period; inferior vena cava (IVC) diameter
- 8) change in breathlessness score using the Likert scale.
- 9) time to clinical euvolaemia and end of intravenous therapy

10) length of stay

11) rate of adverse reactions, serious adverse reactions and suspected unexpected serious adverse reactions – treatment arm

- 12) rate of adverse events and serious adverse events both arms
- 13) rate of recruitment to study
- 14) time taken to screen & recruit
- 15) rate of drop-out after randomisation cause specific
- 16) Cause specific hospitalisation or mortality after 30 days and 180 days follow up.

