#### Exclusion criteria

1) Unable to give informed written consent

2) Allergy or contraindication to carbonic anhydrase inhibitors

3) Patient thought to be at end-of-life

4) Concurrently taking thiazide (or thiazide-like) diuretic or sodium-glucose linked transporter-2 inhibitor, high dose aspirin (>500mg / day), methotrexate, lithium, or sodium valproate, oral steroids Sando-K®, oral sodium bicarbonate, or other sodium tablets

5) Severe anaemia (haemoglobin <8 g/DL); or severe infection (investigator opinion).

6) SBP <80 mmHg at randomisation

7) Serum sodium (severe hyponatraemia) <130 mmol/L at randomisation

8) Serum potassium (hypokalaemia) <3.5 mmol/L at randomisation

9) Serum chloride (severe hyperchloraemia) >110 mmol/L at randomisation

10) Severe renal dysfunction with an eGFR (estimate glomerular filtration rate) result of  $\leq$ 20 ml/min calculated by the Cockcroft-Gault formula

12) Pregnant or breast feeding, or intends to become pregnant whilst taking part in the trial

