# 8.9 Trial restrictions

There are no dietary requirements or restrictions however patients will be required to complete diet sheets detailing all oral intake during the study. Starting sodium-glucose co-transporter 2 inhibitors or thiazide and thiazide-like diuretics will be contraindicated during the 4 days of treatment with ACZ unless the patient is deemed euvolaemic and ready for discharge in which case it may be clinically appropriate to start an SGLT2I for morbidity and mortality benefit if the patient has left ventricular systolic dysfunction – this decision would be taken by the treating team and not the study team.

Patients with COVID-19 infection which is **not** thought to be contributing to their symptoms – incidental diagnosis – are still eligible for the trial. Similarly, if a patient becomes COVID-19 positive during the study they can continue.

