# 10.3.3 Secondary outcome analysis

Secondary outcomes are exploratory and none are powered for statistical significance. Secondary outcomes that are measured as continuous variables (difference in daily urine output; difference in weight from baseline to day 4; difference in change in serum sodium potassium, bicarbonate, urea, creatinine, and estimated glomerular filtration rate between baseline and day 4; urinary electrolyte concentrations at day 2 and day 4; inferior vena cava diameter; change in breathlessness score (Likert scale); time to clinical euvolaemia; and length of stay) will be assessed using independent samples t-test, and unadjusted linear regression (with treatment assignment as the independent variable), and linear regression adjusted for daily salt intake and median number of hours of furosemide per day.

Secondary outcomes that are measured as categorical variables (incidence of hyponatraemia, hypochloraemia, hypokalaemia, metabolic alkalosis (serum bicarbonate concentrations >29 mmol/L) or metabolic alkalosis (serum bicarbonate concentrations <23 mmol/L); clinical assessment of congestion; proportion of patients with IVC diameter >2cm; proportion of patients with JVD ratio <4; rate of adverse and serious adverse events; rate of drop-out after randomisation will be assessed using chi-squared tests, un-adjusted logistic regression (with treatment assignment as the independent variable), and logistic regression adjusted for daily salt intake and median number of hours of furosemide per day.

Survival analysis (time to cause specific hospitalisation and time to cause specific mortality) will be conducted with a time-to-first event analysis using Kaplan-Meier and logrank tests, un-adjusted Cox proportional-hazard outcome models.

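### Section 9.2 counts a judged need for more diuretic as an SAE, so the between-arm SAE comparison mixes treatment failure with harm and may not treat the arms alike

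*Protocol*

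**What the plan says.** The table in protocol section 9.2 has a group of SAEs for deterioration in condition during the trial. One of them is "Deemed to need escalating doses of loop diuretic or the addition of a second diuretic agent such as thiazide diuretic". The same wording applies to both arms, and the trigger is a judgement of need.

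Section 3.5 makes the "rate of adverse events and serious adverse events both arms" a secondary outcome. Section 10.3.3 says how it is compared: "rate of adverse and serious adverse events; rate of drop-out after randomisation will be assessed using chi-squared tests", with logistic regression on treatment assignment as well.

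The primary hypothesis in section 3.2 concerns "The addition of 250mg acetazolamide orally twice-daily to 240mg / 24hr IV furosemide infusion" and predicts more diuresis. One arm therefore receives a loop diuretic plus acetazolamide, and the other a loop diuretic alone.

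On thiazides, the exclusion criteria in section 6 remove patients "Concurrently taking thiazide (or thiazide-like) diuretic or sodium-glucose linked transporter-2 inhibitor" at entry, in both arms. During treatment the relevant sentence is in section 8.9: "Starting sodium-glucose co-transporter 2 inhibitors or thiazide and thiazide-like diuretics will be contraindicated during the 4 days of treatment with ACZ", with an exception for patients who are euvolaemic and ready for discharge. No parallel sentence is addressed to control patients. Section 1 gives the clinical background for loop-diuretic resistance: "Current guidelines recommend the addition of a thiazide (or thiazide-like) diuretic". Section 7.4 states that the trial is open label.

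**The concern.** A safety comparison should show whether the drug harms patients. Section 2.2 names the harms feared from the combination: hyponatraemia, symptomatic hypotension and renal dysfunction. Section 4 gives feasibility and tolerability as the primary aim, and section 2 says the results will be used to design a larger trial, so the SAE comparison will be read.

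Needing more diuretic is mainly a sign that treatment is not working. If acetazolamide does what the trial hopes, fewer patients on it should meet this item, and that benefit is subtracted from whatever harm the drug causes. The pooled SAE rate could then look level while other serious events are more frequent on acetazolamide.

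Two further features make the item a poor basis for comparing arms. It depends on an opinion formed with the allocation known. And the phrase about a second agent does not mean the same thing in both arms, because one arm already has a second diuretic by randomisation.

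**Working it through.** The protocol states no SAE rate, escalation rate or power for SAEs, so there is no figure to reproduce. The check has a textual part and an illustration under assumed rates.

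**Text, arm by arm**

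- *Loop-escalation limb (9.2).* Worded identically for both arms; no asymmetry by definition.
- *Second-agent limb (9.2).* In control, any agent added to furosemide is a second one. In the acetazolamide arm the second agent is the study drug and is not an event. A thiazide there would be a third agent, and the protocol does not say whether it counts.
- *Thiazide restriction (8.9).* Worded by reference to treatment with acetazolamide. It can be read as covering that arm only, or as naming the 4-day period for everyone.
- *Overdose limb (9.2).* Furosemide above 240 mg IV per day is also an SAE. The trial infusion is 10 mg/hr × 24 h = 240 mg, so raising it for clinical reasons can be recorded as an overdose too. Section 9.9 removes a patient receiving an overdose from analysis.

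**Illustration 1: can harm be offset?** Let b be the rate of other SAEs and c the rate of meeting the escalation item. Assuming independence, pooled rate = 1 − (1 − b)(1 − c). All rates below are assumptions. Other SAEs are 10% on control and 20% on acetazolamide, a true excess of 10 points.

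| Escalation, control v acetazolamide | Control, pooled | Acetazolamide, pooled | Excess on acetazolamide |
|---|---|---|---|
| 20% v 20% | 1 − 0.9 × 0.8 = 28% | 1 − 0.8 × 0.8 = 36% | 8 points |
| 20% v 10% | 1 − 0.9 × 0.8 = 28% | 1 − 0.8 × 0.9 = 28% | 0 |
| 30% v 10% | 1 − 0.9 × 0.7 = 37% | 1 − 0.8 × 0.9 = 28% | −9 points |
| 10% v 20% | 1 − 0.9 × 0.9 = 19% | 1 − 0.8 × 0.8 = 36% | 17 points |

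The same excess of other SAEs can be shown, hidden, reversed or exaggerated, depending on the escalation rates.

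**Illustration 2: how much could uneven counting add?** Take b = 10% in both arms, the same underlying escalation rate c in both, and let a share s of those events go uncounted on acetazolamide. Control minus acetazolamide = (1 − b) × c × s. I use 20 per arm, from the minimum of 40 patients and 1:1 allocation.

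- s = 0: difference 0.
- c = 10%, s = 25%: 0.9 × 0.10 × 0.25 = 2.25 points, about 0.4 of an event per 20 patients.
- c = 40%, s = 50%: 0.9 × 0.40 × 0.50 = 18 points, 3.6 events per 20.
- s = 100%, c = 10% to 40%: 9 to 36 points, 1.8 to 7.2 events per 20. This is an extreme case, since it requires that no acetazolamide patient is ever counted, although the loop limb is open to them.

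**The case against.** A reader might infer that the SAE comparison is tilted against control, because acetazolamide patients cannot score the item and are the only ones barred from a thiazide. The documents do not support that.

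- The trigger is judged need, not receipt. A bar on starting a thiazide does not stop a patient being judged to need one.
- The loop-escalation limb is open to both arms on the same words.
- The sentence in 8.9 sits under general trial restrictions and may cover everyone. Nothing says control patients may start a thiazide, and the remark in section 1 is background.
- Direction is not shown. Acetazolamide overdose is an SAE possible only in that arm, and open-label judgement could move either way.
- Fewer escalations on an effective drug would be a true treatment effect, not a definitional artefact.
- Some escalations may meet section 9.1, by prolonging hospitalisation or as important medical events.
- Hyponatraemia incidence and renal function are compared separately (3.5, 10.3.3), every SAE carries full details (9.4), and secondary outcomes are exploratory and unpowered.

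All of this stands, and it rules out a claim of demonstrated bias. It does not make the pooled comparison sound. A genuine efficacy effect inside a safety endpoint still offsets harm there, as the 28% v 28% example shows. Separate sodium and renal endpoints limit what can be hidden, but hypotension has no between-arm endpoint of its own in 3.5 and is compared only through the AE and SAE rates. The meaning of a second agent on acetazolamide remains undefined.

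**Conclusion.** The point holds as one of mixed content and potential asymmetry. Section 9.2 places an open-label judgement of treatment failure, the inverse of the diuresis hypothesis, inside the SAE rate that 10.3.3 compares between arms. The second-agent wording is not neutral between arms, and 8.9 leaves unclear whom the thiazide restriction covers.

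The size is unknown. It depends on escalation and SAE rates that the protocol does not give. Under assumed rates and independence, a doubling of other SAEs from 10% to 20% can vanish (28% in both arms). Uneven counting alone could add nothing, or 2 to 18 points at 25% to 50% non-counting with a 10% base rate and 10% to 40% escalation. No net direction can be claimed. Because the comparison is exploratory, this is an inexpensive improvement to what the safety table can show, not a threat to the primary analysis.

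**What to change.** In section 10.3.3:

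1. Report need for diuretic escalation (more loop diuretic, or an added agent) by arm as its own outcome.
2. Make the between-arm SAE comparison without this component, except where the event also meets a section 9.1 seriousness criterion.
3. Treat furosemide above 240 mg/day that arises from clinical escalation in the same way, so that it does not re-enter the comparison as an overdose SAE.
4. Show the all-SAE rate by arm alongside.

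Sections 8.9 and 9.2 must be reconciled on whom the thiazide restriction covers and on what counts as a second agent in each arm. Which clinical rule applies is for the sponsor and investigators to settle. Reporting of these events to the sponsor stays as it is.

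The cost is one analysis definition and one extra table row. No new data are needed, because the SAE form already carries the case description and seriousness criteria (9.4). The downside is fewer events in the SAE comparison.
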